### 17.2 Determination of sample size

No formal sample size calculation has been performed. Based on previous clinical studies using the method for dental plaque acidogenicity (studies SM17-02 and SM22-01) (5, 6), a total of 12 subjects are considered sufficient to generate data that can detect a clinically significant increase in plaque acidogenicity for the two prototype products versus the reference product Dry 3 mg NP.

### 17.3 Analysis data set

#### 17.3.1 *Full analysis set*

The Full Analysis Set (FAS) will consist of all subjects who have been randomized. This population will be used as the safety analysis set.

### 17.4 Description of study population

#### 17.4.1 *Demographics and baseline characteristics*

Demographics, as well as the history of nicotine use, will be presented by descriptive statistics and listings.

#### 17.4.2 *Medical/surgical history and prior/concomitant medication*

Medical/surgical history will be presented by system organ classes (SOC) and preferred term (PT). Prior/concomitant medications will be presented by ATC level 1, 3 and 5 through descriptive statistics and listings.

#### 17.4.3 *Usage compliance*

The number of subjects using the IPs will be presented by descriptive statistics and listings.

#### 17.4.4 *Oral examination*

Any abnormal findings at screening, *i.e.*, judged as outside the normal ranges by the Investigator, will be categorized as “abnormal, not clinically significant” or “abnormal, clinically significant” and presented in listings.

### 17.5 Analysis of the primary endpoint

#### 17.5.1 *Difference in dental plaque acidogenicity*

The primary endpoint is the difference in dental plaque acidogenicity, assessed by measuring pH in plaques after short-term exposure (45 minutes) to three different Dry 3 mg NPs. The assessment of dental plaque acidogenicity will be calculated at each time point and presented with summary statistics, including the average for all four sites and the average per site, as described in Section 17.1.

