On the first usage visit (Visit 2), subjects will be randomized to one of three usage sequences. During each usage visit (Visits 2-4), the subjects will place the IP in their upper vestibulum, where they normally place their pouches, using their fingers. The IP will be kept in place for 45 minutes. Dental plaque acidogenicity will be assessed by measuring pH in the plaque at four different locations before placement (baseline), and at 2, 5, 10, 15, 20, 30, and 45 minutes afterwards. All pH assessments will be performed on the same side as the IP placement.

The salivary buffer capacity will be assessed at baseline (0 minutes), and at 15, 30, and 45 minutes. Unstimulated saliva will be collected at each time point.

The effects on the oral mucosa from the usage of each IP will be assessed before (baseline) and after 45 minutes of usage. The effects, in the form of redness and mechanical irritation, will be graded as: no effect, mild effect, and severe effect. Photos will be taken before and after the usage of each IP to enable a more detailed comparison on the effects.

The subjective salivary stimulation effect of each IP will be evaluated after 30 minutes of use using a 100 mm VAS, anchored with “no effect” to “extremely large effect”.

AEs will be collected by subject interview and those spontaneously reported by the subjects from the first usage visit (Visit 2) to the last usage visit (Visit 4).

See Table 8.1-1 for the schedule of events applicable for each visit. Study assessments are described in Section 11.

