## 11.3 Assessment related to the primary endpoint

### 11.3.1 *Dental plaque acidogenicity*

An iridium microelectrode (Beetrode) will be inserted into the plaque at four different locations: 1) immediately mesial to the pouch, 2) immediately distal to the pouch, 3) interproximal between the front tooth/canine (tooth 13 and 12 or tooth 22 and 23), and 4) interproximal between the premolar/molar (tooth 16 and 15 or tooth 25 and 26). The electrode will be connected to a pH meter (Orion SA720 pH/ISE Meter) along with a reference electrode. The reference electrode will be placed into a solution of 3 M KCl with the subject's finger placed in the solution to create a salt bridge.

After calibration and baseline assessment (0 minutes), the subjects will place the IP in their mouth and use it for 45 minutes. The pH will then be measured at 2, 5, 10, 15, 20, 30, and 45 minutes on the same side as the IP placement. In case of difficulties in acquiring microelectrodes, the strip method will be used; a paper indicator strip will be inserted in the area and kept in place for 10 seconds, after which the color change will be manually compared with a color scale. The date and time of collection of each sample and the assessed pH values will be recorded in the CRF.

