### 17.1 General

Descriptive analysis will be performed to calculate the mean  $\pm$  standard deviation. Statistical analysis between the different products will be conducted for the various variables using two-way ANOVA followed by Tukey's HSD test. The relationship between the different collected variables will be analyzed using Pearson correlation coefficient. All analysis will be performed using PRISM 8 (GraphPad Software, San Diego, CA, US). A p-value  $<0.05$  is considered statistically significant.

No adjustment for multiple comparisons will be made.

No imputation of missing data will be performed.

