### 17.6 Analysis of secondary endpoints

#### 17.6.1 *Buffer capacity*

The difference in salivary buffer capacity, assessed in unstimulated saliva after short-term exposure (45 minutes) to three different Dry 3 mg NPs, will be calculated at each time point and presented with summary statistics, as described in section 17.1.

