### 17.7 Analysis of exploratory endpoint

#### 17.7.1 *pH levels in saliva*

The difference in pH levels in unstimulated saliva, assessed using a pH meter, after short-term exposure (45 minutes) to three different Dry 3 mg NPs, will be calculated at each time point and presented with summary statistics, as described in Section 17.1.

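### The stated primary analysis makes no use of the plaque pH read before placement at every usage visit; using it as a covariate could sharpen the product comparison

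*Protocol*

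**What the plan says.** Section 8.1 describes "measuring pH in the plaque at four different locations before placement (baseline), and at 2, 5, 10, 15, 20, 30, and 45 minutes afterwards". Section 11.3.1 confirms the order: "After calibration and baseline assessment (0 minutes), the subjects will place the IP in their mouth and use it for 45 minutes". A pre-exposure reading therefore exists for every subject, site and usage visit.

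Section 17.5.1 defines the endpoint without mentioning baseline: "The primary endpoint is the difference in dental plaque acidogenicity, assessed by measuring pH in plaques after short-term exposure (45 minutes"). It continues: "The assessment of dental plaque acidogenicity will be calculated at each time point", with summary statistics as a four-site average and for each site, and refers to Section 17.1 for the method. Section 17.1 reads: "Statistical analysis between the different products will be conducted for the various variables using two-way ANOVA followed by Tukey's HSD test". It also fixes the significance level and the software. It does not name the two ANOVA factors.

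Buffer capacity (Section 17.6.1) "will be calculated at each time point and presented with summary statistics, as described in section 17.1". Salivary pH (Section 17.7.1) is worded the same way. None of these sections mentions a change from baseline, a covariate or a baseline-corrected summary.

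**The concern.** The crossover removes stable differences between subjects, but not differences between one subject's visits. The protocol gives reasons to expect the starting pH to vary between visits. Plaque builds up at home during 12 to 24 hours without cleaning, and subjects may use their own snus or pouches until one hour before (Sections 8.1 and 9.6.1). Section 6.1 itself reports that tobacco-based snus can lower biofilm acidogenicity.

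If the starting level carries through to the later readings, part of any observed product difference reflects where each visit began. With 12 subjects and no formal sample size calculation (Section 17.2), there is little precision to spare. The study is meant to detect an increase in acidogenicity for the prototypes, so imprecision makes a real increase easier to miss.

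**Working it through.** **Inputs from the protocol.** 12 subjects (Section 17.2); three sequences ABC, BCA, CAB (Section 9.9); significance at 0.05 (Section 17.1). No effect size, SD, power or sidedness is given, so the choice of 12 cannot be reproduced.

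**Assumptions.** Two-sided test; four subjects per sequence; one post-placement pH value per subject and visit (a single time point or an average); equal within-subject variance at baseline and afterwards; one pairwise contrast without Tukey widening. Let sigma_w be the within-subject, visit-to-visit SD of pH. Let rho be the correlation between a visit's baseline and later pH beyond the subject effect. It is not in the protocol, so 0 to 0.7 is shown.

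**Size of chance imbalance.** The SE of the difference between two products' mean baselines is sigma_w × √(2/12) = 0.41 sigma_w. An unadjusted comparison carries, on average, rho times whatever imbalance occurs.

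**Variance of a product difference relative to unadjusted pH.**
- Change from baseline: 2(1 − rho).
- Baseline as covariate: 1 − rho², before the cost of estimating its slope.
- With that cost: 36 values less 12 subject, 2 period and 2 product parameters leave 20 df, and the factor is 1 + 1/(20 − 2) = 1.056.

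| rho | Change score | Covariate, before cost | Covariate, with cost | Equivalent n, 12 ÷ (with cost) |
|---|---|---|---|---|
| 0 | 2.00 | 1.00 | 1.06 | 11.4 |
| 0.3 | 1.40 | 0.91 | 0.96 | 12.5 |
| 0.5 | 1.00 | 0.75 | 0.79 | 15.2 |
| 0.7 | 0.60 | 0.51 | 0.54 | 22.3 |

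The covariate breaks even where (1 − rho²) × 19/18 = 1, so rho² = 1/19 and rho is about 0.23.

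**Simulation check.** 4,000 runs per setting, with subject, period and product in the model. The true difference was 1.2 sigma_w, which is what unadjusted pH detects with 80% power on 20 df.

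| rho | Power, unadjusted | Power, change | Power, covariate |
|---|---|---|---|
| 0 | 80% | 50% | 78% |
| 0.3 | 81% | 67% | 82% |
| 0.5 | 79% | 80% | 87% |
| 0.7 | 80% | 95% | 97% |

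With no true difference, all three analyses averaged within 0.01 sigma_w of zero and rejected in 4.5% to 5.5% of runs.

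**The case against.** **The point rests on silence.** Section 17 announces only the principal features, and a SAP, not shown here, may add a covariate. Calculating acidogenicity at each time point could also be read as covering a change score, and text next to the endpoint definition in Section 7.1.1 is redacted. This stands as a limit on wording: one can say that the protocol states no adjustment, not that none will be made. It does not remove the point, because the protocol already fixes the measured variable, the test, the post-hoc procedure and the software, and the baseline appears in none of them.

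**The design already standardises the start.** Visits are at the same time of day, with fixed abstention from cleaning, food, drink and nicotine. That may reduce the variation in starting pH. How much is left, and how strongly it predicts later pH, cannot be told from the protocol.

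**A reader might infer bias**, with visit differences confounded with product. The documents do not support that. Each product occurs once in each period and sequences are randomized, and the simulation shows the unadjusted comparison centred on zero with its type I error held.

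**A reader might also infer dilution**, with the 0-minute reading counted as one of eight outcome levels so that a constant product effect shrinks to 7/8. This needs the ANOVA factors to be product and time, 0 minutes to be a level, and the product main effect to be the test. Section 17.1 does not name the factors. Under that same model the product-by-time interaction would reflect change from baseline, although Tukey comparisons of products at each time point would remain unadjusted.

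**Conclusion.** The point holds as one of efficiency. A baseline is collected at every usage visit, and the stated analysis does not use it. The gain from using it is conditional on rho: a loss of about 2 power points if rho is near 0, close to nothing at 0.3, and material from 0.5 upwards (79% to 87% at 0.5 and 80% to 97% at 0.7, for a true difference of 1.2 sigma_w). It would be wrong to say that adjustment narrows every interval, since below a rho of about 0.23 the expected variance rises slightly. The possible loss is small and the possible gain large, so adjustment is the better pre-stated choice. Stating it before data exist also prevents a later selection among unadjusted pH, change and covariate-adjusted results. The figures rest on the assumptions listed with the calculation, above all the unknown rho.

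**What to change.** In Section 17.5.1, state that products are compared on post-placement pH, with 0 minutes excluded from the outcome, in a model with subject, period, product and the visit's own 0-minute pH as covariate. Use the four-site mean baseline for the overall analysis and the same site's baseline for the per-site analyses. Fit subject as a fixed effect; if it is random, add the subject's mean baseline so that the slope is a within-subject one. Do the same in Section 17.6.1 with the 0-minute buffer capacity, and in Section 17.7.1 if salivary pH is analysed, since Section 7.3 allows the exploratory results to go unreported. Do not substitute plain change from baseline.

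The cost is about a sentence per endpoint, one model df, the small power loss if rho is near 0, and a check that the software named in Section 17.1 can fit the model. No new data are needed. The change should be made before database lock.

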## 8 STUDY DESIGN

### 8.1 Overall study design and schedule of events

This is an open-label, randomized, 3-way crossover, single administration study designed to assess the effects on dental plaque acidogenicity after using Dry 3 mg NPs, [REDACTED] in current daily users of NP or tobacco-based snus. The IPs are one Dry 3 mg NP (reference product) and two prototype products [REDACTED]. [REDACTED]. [REDACTED]

The study will include 12 randomized and fully evaluable subjects. Healthy male and female subjects aged  $\geq 21$ - $\leq 55$  years who have used NP or tobacco-based snus for  $\geq 1$  year, with a minimum weekly consumption of 3 cans, may be eligible for participation. An effort will be made to randomize at least 3 female subjects (25%).

The subjects will visit the test laboratory on four occasions, with at least three days between each visit. Each visit will last approximately 1.5 hours. Consequently, each subject is expected to participate in the study for about two weeks, excluding the screening period.

The subjects will report to the test laboratory for a screening visit (Visit 1), which will take place within four weeks prior to the first usage visit (Visit 2). This screening visit will involve an eligibility check, including evaluations of smoking and oral tobacco/nicotine use, a brief oral examination, urine pregnancy testing (for women of childbearing potential only), and collection of medical history. Additionally, the salivary secretion rate, buffer capacity, and the number of cariogenic bacteria (*Streptococcus mutans* and lactobacilli) will be assessed.

Before each usage visit (Visits 2-4), scheduled at the same time of day for each subject, the subjects will refrain from approximal tooth cleaning for 24 hours and toothbrushing for 12 hours prior to the visits. Additionally, subjects will be instructed not to eat, drink, chew gum, use nicotine-containing products (including smoking), or engage in any other mouth-related procedures 1 hour before the visits. Subjects will use their regular toothbrush, which may be manual or electric, throughout the study. Urinary pregnancy tests may be conducted at Visits 2-4 for women of childbearing potential.

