**Table 8.1-1 Schedule of events**

Events	Visit 1 Screening	Visit 2 First usage visit	Visits 3-4 Second and third usage visit
Informed consent	X		
Demographics	X		
Medical/surgical history	X		
History of nicotine use	X		
Inclusion/exclusion criteria	X	X 	
Brief oral examination	X	X	X
Salivary secretion rate	X		
Salivary buffer capacity	X	X	X
Pregnancy test 	X	X 	X 
Baseline symptoms	X	X	
Prior and concomitant medications		X	
Randomization		X	
Administration of IP		X	X
Plaque acidogenicity 		X	X
Oral mucosa effects		X	X
VAS question		X	X
Collection of saliva		X	X
AEs		X	X

Confirmation of eligibility criteria.

Only women of childbearing potential.

Only at the discretion of the Investigator on Visits 2-4.

Assessed at 0, 2, 5, 10, 15, 30, and 45 minutes.

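### No single primary plaque-pH quantity is fixed (up to 35 time-by-site quantities), and Section 17.1 names Tukey's HSD while ruling out multiplicity adjustment

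*Protocol*

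**What the plan says.** Section 17.5.1 describes the primary endpoint as the difference in plaque acidogenicity, measured as plaque pH, after 45 minutes of use. It then says that this "will be calculated at each time point and presented with summary statistics, including the average for all four sites and the average per site", and refers to Section 17.1 for the method.

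Section 17.1, repeated in the synopsis, prescribes two-way ANOVA and Tukey's HSD between products, with p<0.05 as the threshold. It does not name the two factors. The same section states "No adjustment for multiple comparisons will be made".

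On the dimensions of the data:

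- **Sites (11.3.1):** the electrode "will be inserted into the plaque at four different locations".
- **Times (11.3.1):** "The pH will then be measured at 2, 5, 10, 15, 20, 30, and 45 minutes". The synopsis and Sections 8.1 and 11.1 list the same times.
- **Times (Table 8.1-1, footnote 4):** "Assessed at 0, 2, 5, 10, 15, 30, and 45 minutes". The 20-minute reading is absent, although Section 11 sends the reader to this table for timing.
- **Products (8.1):** "The IPs are one Dry 3 mg NP (reference product) and two prototype products".

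Section 17.2 frames the aim as detecting a rise in acidogenicity for the two prototypes against the reference.

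**The concern.** A primary endpoint should reduce to one pre-stated quantity, or to several with a stated rule for combining them. Section 17.5.1 gives a grid of times by sites and no rule. Section 17.1 attaches a significance threshold to product comparisons and disclaims adjustment, while naming a procedure that is itself an adjustment. The intended error control therefore cannot be read from the text.

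At stake is the study's main conclusion. If several p-values count as primary, a chance difference at one time or site can be reported as a prototype effect. The answer then depends on which cell is highlighted, and the overall error rate is unknown.

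**Working it through.** The plan states no familywise error rate and no formal sample-size calculation, so there is no figure of its own to reproduce. The check counts the quantities and then asks what error rate follows.

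**Inputs.** Post-placement times: 7 (11.3.1), or 6 on the Table 8.1-1 footnote. Site summaries: 4 sites + 1 average = 5 (17.5.1). Products: 3, hence 3 pairs (8.1). Subjects: 12 (17.2). Threshold: 0.05 (17.1). Correlations between sites and times are not given, so they are assumed and varied.

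**Count.** 7 × 5 = 35 time-by-site quantities, each a family of 3 product pairs. On the footnote's times it is 6 × 5 = 30.

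**Independence benchmark.** With Tukey holding each family at 5%, the chance of at least one false difference over m independent families is 1 − 0.95^m:

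- m = 35: 0.834
- m = 30: 0.785
- m = 7 (four-site average only): 0.302

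These are reference values only. The readings are correlated, and one of the five summaries is the mean of the other four.

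**Simulation with correlation.** No true product difference; 12 subjects each using 3 products; 4 sites plus their mean; 7 times; 4,000 runs per scenario. Each cell is tested with a subject-blocked analysis on (12 − 1)(3 − 1) = 22 error degrees of freedom. A pair is declared different under Tukey when |t| exceeds q/√2 = 2.512 (the unadjusted limit would be 2.074). Each entry gives AR(1) / equal correlation over time.

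| Correlation: sites, times | All 35 cells | Four-site average, 7 times |
|---|---|---|
| 0, 0 | 81.6% / 81.2% | 30.4% / 30.4% |
| 0.3, 0.3 | 73.6% / 71.7% | 28.7% / 27.9% |
| 0.5, 0.5 | 67.5% / 61.8% | 28.3% / 24.0% |
| 0.5, 0.7 | 60.9% / 51.3% | 24.2% / 18.7% |
| 0.7, 0.7 | 54.0% / 44.5% | 23.8% / 19.0% |
| 0.8, 0.8 | 41.6% / 33.7% | 20.3% / 15.7% |
| 0.9, 0.9 | 27.5% / 22.0% | 15.6% / 12.5% |

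A second simulation let correlation decay with elapsed time (0.5 to 0.9 per 10 minutes, 0.3 to 0.8 between sites). With Tukey it gave 29 to 67% over the grid and 13 to 26% for the four-site average.

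**After reduction to one quantity.** Testing only the four-site average at 45 minutes with Tukey gave 4.6 to 5.2% across all scenarios. Keeping the whole grid as primary would instead need about 0.05/35 = 0.0014 per family under Bonferroni.

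**The case against.** **Section 17.5.1 may describe tabulation, not 35 separate tests.** It speaks of summary statistics. If the unnamed ANOVA factors are product and time, one model could yield one overall product test. This stands in part: the size of the test family is undefined, and 35 is its upper reach. But the section invokes the testing rules of Section 17.1, no overall test is made primary, and the five site summaries would remain in any case.

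**Tukey's HSD already adjusts.** This stands for the three product pairs. A reader might count 35 × 3 = 105 unadjusted comparisons and quote a false-positive chance of 51 to 92%. That sets aside a procedure the protocol names, so the Tukey figures are the fair ones. Tukey within a cell does nothing across times and sites, however.

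**The SAP can settle it, and parts of the endpoint wording are redacted.** Choosing a summary variable can be left to an SAP. An explicit no-adjustment rule beside Tukey, with a primary analysis spread over times and sites, is stated in the protocol itself. The redactions affect the synopsis and Section 7.1.1; the readable text of Section 17.5.1 names no single quantity.

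**A false signal of harm is the cautious error in a risk assessment.** This is fair as to direction, but it does not give the reported result a known error rate.

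**The 20-minute footnote is clerical.** Agreed. It is a small inconsistency and does not support the multiplicity argument. It matters here only because it changes which readings enter the primary variable.

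**Conclusion.** The concern holds in this form: the primary quantity and its family of tests are not fixed, and Section 17.1 contradicts itself on adjustment. If every time-by-site cell is tested with Tukey, the chance of at least one false difference is roughly 20 to 70% for correlations of 0.5 to 0.9, and about 13 to 28% for the four-site average alone, against a nominal 5%. These figures rest on assumed correlations, normal errors and a separate subject-blocked test in each cell, none of which the protocol specifies.

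Two stronger conclusions are tempting and are not supported. A reader might infer that a chance finding is likely, meaning more probable than not. With Tukey over the full grid, that holds only at low to moderate correlation; at 0.9 it is 22 to 28%. A reader might also infer that the sponsor could not rule out a prototype effect. Multiplicity inflates false positives; ruling out an effect depends on a margin and on precision, which is a different question.

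**What to change.** 1. In Sections 7.1.1 and 17.5.1, name one primary variable per visit. One example is the baseline-adjusted time-weighted mean pH over 0 to 45 minutes of the four-site average. Another single pre-stated summary would also cure the defect.
2. Compare each prototype with the reference at an overall 5% error rate, using Tukey or Dunnett. Two comparisons each at an unadjusted 5% could reach up to 2 × 0.05 = 10%.
3. Make per-time, per-site and minimum-pH results supportive: estimates with confidence intervals and no significance claims.
4. Replace the no-adjustment sentence in Section 17.1 and the synopsis so that it agrees with item 2.
5. Reconcile Table 8.1-1 footnote 4 with the 20-minute reading in Sections 8.1, 11.1 and 11.3.1, so that the primary variable uses the same readings throughout.

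The cost is protocol wording and one footnote, with no extra subjects, visits or measurements. The downside is small but real: averaging over time and sites can dilute a brief or local pH fall, and such findings become supportive only.
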